| Concomitant medications and concurrent procedures (TI) Continuous monit |  | torin                   | g                        |  |                          |                           |

Tx = treatment

a Randomization must occur within 30 days of screening; screening visit and randomization visit can occur on the same day if participants do not require washout. If screening and randomization visits occur on the same day, inclusion/exclusion criteria, ATHS, and urine pregnancy test need not be repeated.

c For female participants of childbearing potential; administered and confirmed negative prior to study intervention. A female is not considered of childbearing potential if she has been postmenopausal for at least 1 year or does not have a uterus at the time of study entry.

d Done prior to randomization and study intervention.

e Done prior to study intervention.

- f TI will use EI ATHS scores to confirm participant's eligibility in the study.
- g On initial and touch-up treatment days, vision assessments will be performed by TI (or designee) before study intervention and at least 30 minutes after completing last injection procedure.
- h The safety e-diaries are to be completed following each study intervention starting on the day of treatment.

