| Adverse events i  |  |  | Continuou                                    | is monitoring                                |  |  |
| Concomitant medications and concurrent procedures  |  |  | Continuou                                    | s monitoring                                 |  |  |

- a A maintenance treatment is offered to participants who complete the Month 13 visit. The procedures must occur no later than 14 days after the Month 13 visit.
- b Follow-up visit schedule is based on the date of the last study intervention (ie, maintenance treatment).
- c If a participant withdraws for any reason prior to the final study visit, attempts will be made to perform assessments at an exit visit.
- d For female participants of childbearing potential. A female is not considered of childbearing potential if she has been postmenopausal for at least 1 year or does not have a uterus at the time of study entry.
- e Administered and confirmed negative prior to study intervention. If maintenance treatment is done on the same day of the Month 13 visit, this assessment does not need to be repeated.
- f Prior to maintenance treatment. If maintenance treatment is done on the same day of the Month 13 visit, this assessment does not need to be repeated.
- g Vision assessments will be performed by TI (or designee) before study intervention and at least 30 minutes after completing the injection procedures.
- h The safety e-diaries are to be completed following each study intervention starting on the day of treatment.
- i Will include a general, nondirected question about vision symptoms.

a month = 30 days

#### Protocol 1878-702-008 Amendment 2

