#### Table 1-5 Control Group Procedures: Control Period

| Procedure  | Randomization a | Follow-up b |                                     |  |
|--|-----------------------------------|------------------------|-------------------------------------|--|
|  |                                   | Month 1                | Month 3/
Study Exit e |  |
| Visit Window (Days)                                      |                                   | +10                    | ± 7                                 |  |
| Urine pregnancy test d                        | Х                                 |                        |                                     |  |
| ATHS (EI) e                                   | X f                    | Х                      | Х                                   |  |
| Inclusion/exclusion criteria (TI)                        | Xf                                |                        |                                     |  |
| 3D facial digital imaging                                | Xf                                | Х                      | Х                                   |  |
| FACE-Q Satisfaction with Facial Appearance (Participant) | Xf                                | Х                      | Х                                   |  |
| FACE-Q Satisfaction with Temples (Participant)           | Xf                                | Х                      | Х                                   |  |
| Self-perception of age (Participant)                     | Xf                                |                        |                                     |  |
| Jaw Functional Limitation Scale (Participant)            | Xf                                |                        |                                     |  |
| Randomization  | Х                                 |                        |                                     |  |
| GAIS (Participant)                                       |                                   | Х                      | Х                                   |  |
| GAIS (EI)  |                                   | Х                      | Х                                   |  |
| Weight   |                                   |                        | Х                                   |  |

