| Adverse events j (TI)  | Continuous monitoring               |                                 |                           |  |                                 |                           |         |         |         |                 |                                  |
| Concomitant medications and concurrent
procedures (TI)
a month = 30 days: Tx = treatment                          |                                     | Continuous monitoring           |                           |  |                                 |                           |         |         |         |                 |                                  |

a month = 30 days; Tx = treatment

a An optional treatment is offered to control group participants at the Month 3 visit. The optional treatment procedures will be performed after completion of all Month 3 visit procedures. The optional treatment must be completed within 14 days after the Month 3 visit.

If no touch-up treatment is performed, the 30 Days After Initial

Treatment visit becomes the Month 1 visit.

c The follow-up visit schedule is based on the date of the last study intervention (ie, if no touch-up treatment is performed, then Month 1 occurs 30 days after initial treatment; if touch-up treatment is performed, the Month 1 visit occurs 30 days after touch-up treatment).

d If a participant withdraws for any reason prior to the Month 6 visit, attempts will be made to perform assessments along with a urine pregnancy test at an exit visit.

• For female participants of childbearing potential. A female is not considered of childbearing potential if she has been postmenopausal for at least 1 year or does not have a uterus at the time of study entry.

f Administered and confirmed negative prior to study intervention.

[figure not shown]
g Done prior to study intervention.

h On initial and touch-up treatment days, vision assessments will be performed by TI (or designee) before study intervention and at least 30 minutes after completing the injection procedures.

i The safety e-diaries are to be completed following each study intervention starting on the day of treatment.

[figure not shown]
j Will include a general, nondirected question about vision symptoms.

d (Moradi 2011, Sykes 2009).

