1.0 Introduction

This Statistical Analysis Plan (SAP) provides a technical and detailed elaboration of the statistical analyses of the effectiveness and safety data as outlined and specified in the final protocol of Study 1878-702-008 (Amendment 2, 12 May 2021). Specifications of tables, figures and data listings are contained in a separate document.

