8.0 Effectiveness Analyses

8.1 General Considerations

- This section applies to both effectiveness and safety analyses when applicable.
- To account for different timing of VOLUMA XC treatment and comparable time frames of data collection and to enhance interpretability of effectiveness and safety analyses, the statistical analyses will be performed by the study periods defined in Table 2.
- For CP, effectiveness analyses and baseline characteristics will be performed on the mITT population using the as-randomized assignment.

- For TP, effectiveness and safety summaries will be performed on the VT population, using as-treated grouping.
- For MP, effectiveness and safety summaries will be performed on the VMT population.
- Study day refers to Day 1 regardless of study period (e.g., CP, TP, MT).
- The baseline for effectiveness and safety parameters will be the last non-missing assessment prior to or on Day 1, i.e., the latter of randomization or initial injection in Control Period. Day 1 is defined as the day on which the study intervention (VOLUMA XC or no-treatment) is first received.
- The change from baseline values will be computed as the postbaseline value minus the baseline values.
- For vision assessments, baseline will refer to the most-recent measurement just prior to the most-recent treatment.
- Continuous variables will be summarized by number of participants with observed values (n), mean, standard deviation (SD), median, 1st and 3rd quartiles (Q1, Q3), minimum (min), and maximum (max). Categorical variables will be summarized by the number of participants with observed values or events (n) and the percentage of participants with observed values or events.
- All statistical hypothesis tests will be performed at the 2-sided, 5% significance level, unless stated otherwise.
- All CIs will be 2-sided 95% CIs, unless stated otherwise.
- All statistical analyses will be performed using SAS Version 9.4 or subsequent.

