9.8 Procedural Pain

Participant assessment of procedural pain (pain during injection) on an 11-point scale ranging from 0 (no pain) to 10 (worst pain imaginable) after initial, touch-up and maintenance treatment will be summarized. The summary will be performed by treatment group for VT and VMT as described in Table 11.

change represents an improvement, and a negative change represents a worsening. Baseline is the pre-treatment value on or before the most recent treatment.

$$\text{Line change} = 10 \times [\log_{10} (d_{\text{baseline}}/20) - \log_{10} (d_{\text{follow-up}}/20)]$$

where d_{baseline} = denominator of the Snellen equivalent score at baseline,

$d_{\text{follow-up}}$ = denominator of the Snellen equivalent score at follow-up visit

Positive findings in confrontation visual fields assessments (e.g., No is reported for "Is eye full to confrontation?" or Yes is reported for "Is there a change from pre-treatment?"), will be listed.

Positive findings in ocular motility (e.g., No is selected for "Does the eye have full duction and version?" or Yes is reported for "Is there a change from pre-treatment?") will be listed.

[REDACTED]

[REDACTED]

[REDACTED]

Concomitant medications (Section 7.3) and concurrent procedures (coded using MedDRA) will be listed.

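### Does resetting the vision baseline at each treatment hide a cumulative loss of visual acuity?

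*SAP*

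**What the plan says.** SAP 8.1 first sets a general rule: "The baseline for effectiveness and safety parameters will be the last non-missing assessment prior to or on Day 1". It then makes one exception: "For vision assessments, baseline will refer to the most-recent measurement just prior to the most-recent treatment". The text beside the Snellen line-change formula, which follows section 9.8 in the public copy, says the same: "Baseline is the pre-treatment value on or before the most recent treatment".

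The protocol collects the readings that this rule needs. Table 1-2, footnote g, covers the treatment group's initial and touch-up days: "vision assessments will be performed by TI (or designee) before study intervention and at least 30 minutes after completing last injection procedure". Table 1-4, footnote g, covers maintenance: "Vision assessments will be performed by TI (or designee) before study intervention and at least 30 minutes after completing the injection procedures". Table 1-6, footnote h, makes the same provision for controls who take the optional treatment and touch-up. Table 1-5 ("Control Group Procedures: Control Period"), as printed, lists no vision test, and neither does the screening schedule in Table 1-1.

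On outputs, SAP 1.0 states: "Specifications of tables, figures and data listings are contained in a separate document".

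**The concern.** Every other safety parameter is measured from Day 1, while the vision reference moves with each injection. The treatment group may have an initial treatment, a touch-up and a maintenance treatment; controls may have two sessions. After a second or third session, the defined line change leaves out whatever had already been lost. Someone who drops about one line per session would show three small changes and no large one. No readable sentence defines change from acuity before any VOLUMA XC.

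Visual disturbance is the only adverse event of special interest named for this study, and Snellen acuity is a listed safety endpoint. If the moving reference masked a loss, the safety record would look better than it is.

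**Working it through.** **Does the rule contradict itself?** No. Section 8.1 and the sentence at the formula give the same reference, and the exception to the Day 1 rule is explicit. There is also a practical reason for it: with no vision test listed at screening or at control randomization, a Day 1 rule would leave controls without a vision baseline.

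**How often does the reference move?** Count the scheduled readings after the first injection (Tables 1-2, 1-3, 1-4 and 1-6). A reading taken just before touch-up or maintenance is scored against the value before the preceding treatment, which is the plain reading of 8.1.

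| Course | Readings | Reference later than the pre-first-injection value |
|---|---|---|
| Initial only | 3 | 0 |
| Initial and touch-up | 3 + 3 = 6 | 3 |
| Initial and maintenance | 4 + 3 = 7 | 3 |
| Initial, touch-up and maintenance | 3 + 4 + 3 = 10 | 4 + 3 = 7 |
| Control: optional treatment and touch-up | 3 + 3 = 6 | 3 |

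These are readings with a different reference, not misleading readings. If acuity has not changed, both references give zero.

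**Is any change lost?** The SAP formula is: line change = 10 × [log10(d_baseline/20) − log10(d_follow-up/20)]. Negative means worse. When the last reading of one interval is the reference for the next, the middle terms cancel and the intervals sum to the change from first to last. The documents give no acuities, so those below are assumed.

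- Stepwise, 20/20 to 20/25 to 20/30 to 20/40: -0.97, -0.79 and -1.25. Sum -3.01. Direct change from 20/20 to 20/40: -3.01.
- Stepwise with 20/32 in place of 20/30: -0.97, -1.07 and -0.97. Sum -3.01.
- One step, 20/20 to 20/40, then stable: -3.01 and 0.00. The loss is shown in full.
- Loss then recovery, 20/20 to 20/25 to 20/20: -0.97 and +0.97. A single first-to-last change shows 0.00, so here the per-treatment reference reveals more.

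**When could a flag be missed?** Only if the loss is spread over sessions and the summary uses a cut-off above the largest step. On the first path that step is 1.25 lines, so a 2-line or 3-line cut-off would flag no interval although the total is 3.01. A 1-line cut-off would flag the last interval. The readable SAP states no cut-off, so this scenario rests on assumed acuities and an assumed threshold.

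**Can absence be established?** No. The SAP contents list 9.9 (safety subgroups) and 9.10 (other safety analyses). In the public copy the text passes from the Table 11 reference in 9.8 into the middle of a sentence about line change. Table 11, both headings and the opening Snellen paragraph are lost, and redacted lines follow. That paragraph is where summaries, time points and cut-offs would be expected. Text lost in this way cannot be counted as missing from the plan.

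**Is there another route to detection?** Yes. Protocol 10.7.1 makes any visual disturbance an adverse event of special interest, with loss of vision first among its examples. Section 10.7.7 requires reporting within 24 hours. Adverse-event monitoring is continuous and includes an open question about vision (footnotes to Tables 1-3, 1-4 and 1-6). SAP 9.2.3 summarizes and lists these events.

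**The case for a change.** The best case for the concern is the long gap before maintenance. Table 1-3 schedules vision testing at Month 1 and at no later visit, so the next reading comes just before maintenance, about a year on, and becomes the new reference. If it served only as a baseline, a decline to 20/40 during that year would give 0.00 after touch-up and 0.00 after maintenance, against -3.01 overall. Acuity is also the only one of the three vision measures scored purely as a change. Fields and motility are listed on an absolute finding as well.

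Part of this stands. For participants with several sessions, the readable text prints no single figure for the whole course, and such a figure could be produced from data already collected. But the zero result requires leaving the pre-maintenance reading unscored, which 8.1 does not say. At that reading the most recent treatment is the touch-up or the initial injection, so the plain rule scores it against the value before that treatment.

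The added summary would also have weaknesses. A change over more than a year has no untreated comparator and mixes in causes unrelated to the filler. A worst change taken over several readings leans toward loss from measurement error alone.

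**Conclusion.** The concern does not hold. The per-treatment baseline is stated consistently, can be carried out with the scheduled readings, and is a sound way to tie a change in acuity to an injection. No change drops out: each falls in one interval and the intervals sum to the total. The fear of masking needs repeated small losses plus a cut-off larger than each of them, and the documents supply neither. A cumulative table might be welcome, but the plan gives sound results without it, and no primary analysis, error rate or decision rule depends on it.

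This rests on reading 8.1 so that pre-touch-up and pre-maintenance values are scored against the preceding treatment, and on not treating unreadable text as absent. The acuities and cut-offs above are illustrations.

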8.2 Handling of Missing Data

Missing data will be imputed using the following methods for the effectiveness analyses:

- Multiple Imputation (MI): If there are any mITT participants with missing ATHS score at Month 3 on either side of temple, MI by the Fully Conditional Specification (FCS) method will be used to impute the missing data in ordinal scale by treatment group and by side of temple (left and right). [REDACTED]

- For TP, effectiveness and safety summaries will be performed on the VT population, using as-treated grouping.
- For MP, effectiveness and safety summaries will be performed on the VMT population.
- Study day refers to Day 1 regardless of study period (e.g., CP, TP, MT).
- The baseline for effectiveness and safety parameters will be the last non-missing assessment prior to or on Day 1, i.e., the latter of randomization or initial injection in Control Period. Day 1 is defined as the day on which the study intervention (VOLUMA XC or no-treatment) is first received.
- The change from baseline values will be computed as the postbaseline value minus the baseline values.
- For vision assessments, baseline will refer to the most-recent measurement just prior to the most-recent treatment.
- Continuous variables will be summarized by number of participants with observed values (n), mean, standard deviation (SD), median, 1st and 3rd quartiles (Q1, Q3), minimum (min), and maximum (max). Categorical variables will be summarized by the number of participants with observed values or events (n) and the percentage of participants with observed values or events.
- All statistical hypothesis tests will be performed at the 2-sided, 5% significance level, unless stated otherwise.
- All CIs will be 2-sided 95% CIs, unless stated otherwise.
- All statistical analyses will be performed using SAS Version 9.4 or subsequent.

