8.2 Handling of Missing Data

Missing data will be imputed using the following methods for the effectiveness analyses:

- Multiple Imputation (MI): If there are any mITT participants with missing ATHS score at Month 3 on either side of temple, MI by the Fully Conditional Specification (FCS) method will be used to impute the missing data in ordinal scale by treatment group and by side of temple (left and right). [REDACTED]

- **Non-Responder Imputation (NRI):** For sensitivity analysis, the NRI method will categorize any participants with missing Month 3 ATHS scores as non-responders.
- **As Observed (AO):** The AO method will analyze the data based on the observed values without imputation for the missing values. Thus, a participant who does not have an evaluation on a scheduled visit will be excluded from the AO analysis for that visit. The AO method will be used for sensitivity analysis of primary effectiveness endpoint using the OPE population.

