8.3 Primary Effectiveness Endpoint(s) and Analyses

8.3.1 Primary Effectiveness Endpoint(s)

The primary effectiveness endpoint is the ATHS responder status at Month 3 in CP based on EI's assessment. A responder is defined as a participant with at least 1-grade improvement (reduction) from baseline on the ATHS (described in Table 5) on both temples. Each side of temple will be assessed independently by the blinded EI.

Table 5. Allergan Temple Hollowing Scale

Score	Grade	Description
0	Convex	Rounded temple
1	Flat	Flat temple; temporal fusion line may be visible
2	Minimal	Shallow depression or concavity with minimal volume loss; temporal fusion line may be visible
3	Moderate	Moderate depression or concavity with moderate volume loss; moderate prominence of temporal fusion line
4	Severe	Deeply recessed, sunken appearance; marked prominence of temporal fusion line and zygomatic arch

[REDACTED]

[REDACTED]

[REDACTED]

[REDACTED]

[REDACTED]

[REDACTED]

[REDACTED]

[REDACTED]

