8.3.3 Primary Effectiveness Analysis

Primary effectiveness analysis will be performed based on the mITT population. The study intervention will be considered clinically effective if both of these criteria are met:

- The ATHS responder rate for the treatment group is statistically superior to the responder rate for the control group at Month 3
- At least 60% (a point estimate of 60% or greater) of participants treated with VOLUMA XC are ATHS responders at Month 3

For the first criterion, the null and alternate hypotheses are:

$$H_0: P_v = P_c \text{ versus } H_a: P_v \neq P_c$$

where P_v and P_c denote the responder rates for the treatment group at Month 3 after the latest of randomization, initial treatment and touch-up treatment, and control group at Month 3 after randomization, respectively.

If there are no mITT participants with missing scores for the primary effectiveness endpoint, a 2-sided Fisher's exact test with 5% significance level will be used to compare responder rates between treatment and the control group. Otherwise, the methods described in Section 8.3.2 will be applied. If the 2-sided p-value is ≤ 0.05 , which implies that the responder rate between treatment and control is different, and the point estimate of the responder rate for the treatment group is greater than for the control group and is 60% or greater, then treatment will be considered clinically effective. In addition, responder rates and 95% CIs will be calculated for treatment group and control group. No hypothesis testing will be performed for the second criterion.

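### If the SAP imputes missing Month 3 ATHS scores in separate models for each temple, imputed participants will meet the both-temple responder definition too rarely; both temples belong in one model per arm

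*SAP*

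**What the plan says.** SAP Section 8.2 starts the imputation as follows: "If there are any mITT participants with missing ATHS score at Month 3 on either side of temple". The method is FCS multiple imputation, used to "impute the missing data in ordinal scale by treatment group and by side of temple (left and right"). The next text is redacted.

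Section 8.3.3 uses Fisher's exact test if nothing is missing. If anything is missing: "Otherwise, the methods described in Section 8.3.2 will be applied". Section 8.3.2 is not readable either.

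The endpoint these scores feed is defined in Section 8.3.1 for a participant, not a temple: "at least 1-grade improvement (reduction) from baseline on the ATHS (described in Table 5) on both temples".

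Section 8.3.3 then sets two success criteria. One is superiority over control. The other is "At least 60% (a point estimate of 60% or greater) of participants treated with VOLUMA XC are ATHS responders at Month 3", and the SAP states that this one is not hypothesis-tested.

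Sections 8.2 and 8.3.4 add two sensitivity analyses: as observed (AO, in the OPE population) and non-responder imputation (NRI, in the mITT population).

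**The concern.** In Section 8.2 one phrase governs both treatment group and side. Treatment group is plainly a stratifier, so a programmer would reasonably run the two sides separately as well. The left score then does not inform the right.

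The endpoint is a joint event. If the sides are drawn without a link, an imputed participant responds with probability P(left) x P(right). With positively correlated temples this is below P(both). Positive correlation is likely, because the two temples share a face, a treating investigator and an evaluator. If only one temple is missing, a by-side model also ignores the score observed on the other.

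The imputed rate becomes the primary estimate as soon as any score is missing, and it is compared with 60% as a point estimate, with no margin. A low bias could turn a pass into a fail. The control rate would be pulled down too, so the treatment difference would also move.

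**Working it through.** **Inputs from the documents.** The protocol synopsis (Number of Participants) plans 114 and 57 randomized, with 90 and 45 evaluable at Month 3. The implied loss is (114 - 90)/114 = 24/114 = 21.05%, and (57 - 45)/57 = 12/57 = 21.05%. As a check, 90/(1 - 0.21) = 113.9, rounded up to 114. No dropout rate is legible, so this only recovers the planned loss. The documents give no figure for the bias.

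**Assumptions not in the documents.** The missing share equals the planned loss, both temples are missing together, the per-side response rate is m, and the left and right latent responses are bivariate normal with correlation rho.

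**Formula.** With p = P(both temples improve), unlinked imputation gives m² instead of p among imputed participants. Bias in the arm's rate = (24/114) x (m² - p).

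Chance of an estimate of at least 60% ≈ Φ((expected estimate - 0.60)/√(p(1 - p)/114)), first without and then with the bias:

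| m | rho | p | m² | Bias (points) | Chance, linked | Chance, unlinked |
|---|---|---|---|---|---|---|
| 0.75 | 0.4 | 0.607 | 0.5625 | -0.9 | 0.56 | 0.48 |
| 0.75 | 0.6 | 0.635 | 0.5625 | -1.5 | 0.78 | 0.67 |
| 0.75 | 0.8 | 0.669 | 0.5625 | -2.2 | 0.94 | 0.86 |
| 0.80 | 0.4 | 0.676 | 0.6400 | -0.8 | 0.96 | 0.94 |
| 0.80 | 0.6 | 0.699 | 0.6400 | -1.2 | 0.99 | 0.98 |
| 0.80 | 0.8 | 0.729 | 0.6400 | -1.9 | >0.99 | >0.99 |
| 0.85 | 0.4 | 0.749 | 0.7225 | -0.6 | >0.99 | >0.99 |
| 0.85 | 0.6 | 0.767 | 0.7225 | -0.9 | >0.99 | >0.99 |
| 0.85 | 0.8 | 0.791 | 0.7225 | -1.4 | >0.99 | >0.99 |

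Example, second row: 0.2105 x (0.5625 - 0.6345) = -0.0152. The standard error is √(0.6345 x 0.3655/114) = 0.0451. Then Φ(0.0345/0.0451) = 0.78 and Φ(0.0193/0.0451) = 0.67, a loss of 11 percentage points, the largest in the grid. At m = 0.80 or more the loss is under 2 points.

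**Outside the grid.** A simulation of 90 observed and 24 imputed participants gives somewhat larger losses. At a true 60% with rho 0.7 (m = 0.708, below the assumed range) the chance falls from 0.55 to 0.38. At a true 70% it falls from 0.98 to 0.93, and at 75% it stays at about 0.99. For perfectly concordant temples (m = p) at a true 60%, the outer bound on the bias is 0.2105 x (0.36 - 0.60) = -5.1 points.

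**Partial link.** Each temple's own Month 1 status was added as a predictor, at p = 60% and rho 0.7. The bias shrinks from -2.1 to between -2.0 and -0.9 points as the over-time correlation rises from 0.5 to 0.95. It does not vanish.

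**Less missing data.** At 5% missing, the largest bias in the grid is 0.05 x (0.5625 - 0.669) = -0.5 points. At p = 60% and rho 0.5 to 0.9 it is -0.3 to -0.8.

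**Control arm.** At m = 0.15 to 0.25 and rho 0.4 to 0.8 the control rate is also 0.6 to 2.2 points low. With rho 0.9 in both arms, the difference moves by -1.6 points for both-temple rates of 60% versus 10%, and by +1.6 points for 80% versus 30%.

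**The case against.** The strongest objection is the redaction. FCS models each variable conditional on the others included, so the SAP's wording on side can also mean that left and right scores are two variables in one model, each predicting the other. The hidden text may say so. This stands. A reader might infer that the SAP does discard the correlation and that the primary rate is biased; the readable text supports that only as a conditional statement.

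Second, the other temple's score is not the only carrier of the link. GAIS is recorded per participant (protocol Section 8.1.3), and same-side Month 1 scores are themselves correlated across sides. This also stands, but such predictors carry only part of the link.

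Third, on the 60% criterion the bias works against the device and cannot create a false pass. That is correct, but a conservative bias in the primary estimate is still a bias.

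Fourth, AO uses no imputation and NRI counts every missing participant as a non-responder, so a large discrepancy would be visible. Neither replaces the primary estimate on which the decision rests.

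**Conclusion.** The concern holds conditionally. If the sides are imputed in separate models, which is the natural reading of Section 8.2, the treated responder rate is about 0.6 to 2.2 points too low at the planned 21% loss. It is less biased with Month 1 in the model and under 1 point low at 5% missing. The chance of reaching 60% falls by up to about 11 percentage points when the true rate is about 60 to 67%, and by little above 70%.

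These sizes rest on assumed per-side rates, correlation and missingness. A reader might pair a 2-point bias with a true rate of 62% and infer a larger loss. With per-side response of at least 0.75, however, the bias at 62% is at most 0.2105 x (0.62 - 0.5625) = 1.2 points. Lower per-side rates would give more, but the documents state none.

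Nor is 60% a null value under test; it is a threshold for a point estimate. No fixed direction can be claimed for the between-group difference.

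**What to change.** In SAP Section 8.2, specify one FCS model per treatment group, in wide format, containing left and right ATHS at baseline, Month 1 and Month 3, so that each temple predicts the other. Derive both-temple responder status after imputation, within each completed data set. If the redacted model already includes the other temple's scores, delete the reference to side of temple so that the sentence cannot be programmed as separate runs.

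The cost is SAP wording and a small change to the imputation program, with no extra data. The downside is a slightly larger ordinal model in the control arm (57 randomized, 45 expected evaluable), which may need a check for sparse score categories.
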